### 22.4.3 SAMPLE SIZE SUMMARY

With a minimum of 155 in the TearCare group and 155 in the Restasis group, the power for the primary efficacy analysis of TBUT exceeds 90% and provides sufficient precision around the adverse event estimates through 24 months.

## 22.5 STATISTICAL ANALYSIS

### 22.5.1 GENERAL CONSIDERATIONS

The quantitative variables will be summarized using number of subjects (n), mean, median, standard deviation, minimum and maximum. The qualitative variables will be summarized using counts and percentages.

Summaries of all endpoints will be presented by treatment group and visit. Summaries will also be provided for demographics, baseline medical history, concurrent therapies, and subject disposition.

For the purpose of summarization, medical history, concurrent therapies, and adverse events will be coded to MedDRA and WHO Drug dictionaries, as appropriate.

The number of subjects by center will be summarized in a table. Centers with less than 5 enrolled subjects will be combined into a single virtual center for the purpose of statistical analyses.

### 22.5.2 UNIT OF ANALYSIS

Safety endpoints will be analyzed for both eyes. For subject-level effectiveness endpoints, the unit of analysis will be the subject. For effectiveness endpoints assessed on each eye individually, the unit of analysis will be the eye.

### 22.5.3 MISSING DATA

No missing data imputation will be carried out beyond what is built-in to the mixed-effects modeling approach to be used in the primary effectiveness analysis.

No secondary effectiveness endpoints or safety endpoints will be imputed.

### 22.5.4 PRIMARY EFFECTIVENESS ENDPOINTS

#### 22.5.4.1 TEAR BREAKUP TIME

Change from baseline in TBUT will be calculated as visit – baseline such that a positive difference indicates an improvement of dry eye signs. In addition, treatment comparisons between TearCare and Restasis will be calculated as TearCare – Restasis, such that a positive result indicates a better score for TearCare.

Linear mixed effects models will be used to compare the change from baseline in TBUT at the 6 Month visit between TearCare and Restasis. Linear mixed effects models will include fixed terms for baseline TBUT and study site, and a random subject effect to account for within-person correlation (correlation between right and left eyes). The primary analysis will use MCMC imputation to have a full accounting of the ITT population at the 6 Month visit. As supportive analyses, multiple imputation assuming

that data are missing not at random and analyses of observed data only will also be conducted. Two-sample t-tests and Wilcoxon rank sum tests will also be conducted as supportive analyses.

#### **22.5.4.2 TOTAL OSDI**

Change from baseline in total OSDI score will be calculated as visit – baseline such that a negative difference indicates an improvement of dry eye symptoms. In addition, treatment comparisons between TearCare and Restasis will be calculated as TearCare – Restasis, such that a negative result indicates a better score for TearCare.

Change from baseline in total OSDI at the 6 Month visit will be analyzed using ANCOVA models adjusting for baseline and site. Two-sample t-tests and Wilcoxon rank sum tests will also be conducted as supportive analyses.

#### **22.5.4.3 POOLABILITY OF CENTERS**

Poolability of the effectiveness outcomes across centers will be evaluated by testing a treatment-by-center interaction in a separate model using observed data only. If the interaction is significant at  $\alpha=0.15$  a center effect will be included in the final model and results will be reported separately by center.

#### **22.5.5 SECONDARY EFFECTIVENESS ENDPOINTS**

The secondary effectiveness endpoints include change from baseline at 6 Months for the following outcomes:

1. Meibomian Gland Secretion Score
2. Symptom Assessment iN Dry Eye (SANDE) scores
3. Eye Dryness Score
4. Number of Meibomian Glands Yielding any liquid
5. Number of Meibomian Glands Yielding clear liquid
6. Corneal staining scores
7. Conjunctival staining scores
8. Schirmer Score
9. Ocular protection index (OPI): Interblink interval (IBI)/TBUT

All testing of the secondary endpoints will be done using a two-sided alpha of 0.05. We will test the secondary endpoints in the order listed, stopping at the point where a test

fails to reject. This sequential procedure controls the overall type I error rate for the secondary endpoints.

The secondary endpoints can be divided into two groups, those which are measured on a per-eye basis (Corneal Staining, Conjunctival Staining, Meibomian gland scores, Number of Meibomian Glands Yielding any liquid, Number of Meibomian Glands Yielding clear liquid, Blink Rate, Schirmer Score) and those measured on a per-subject basis (OSDI Score, SANDE Scores, Eye Dryness Score).

Endpoints assessed at the eye level will be analyzed with linear mixed effects models adjusting for baseline and site, and with a random subject effect. Two-sample t-tests and Wilcoxon rank sum tests will be conducted on the average of the two eyes as supportive analyses. Endpoints assessed at the subject level will be analyzed using ANCOVA models adjusting for baseline and site, with two-sample t-tests and Wilcoxon rank sum tests as supportive analyses. No imputation will be performed for secondary efficacy variables.

All secondary effectiveness variables collected will be summarized descriptively (n, mean, standard deviation, median, min and max) by treatment group and visit.

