## 22 APPENDIX B – STATISTICAL ANALYSIS PLAN

### 22.1 ANALYSIS POPULATIONS

- Intent-to-Treat Population - The intent-to-treat (ITT) population includes all randomized subjects. The primary and secondary efficacy analyses will be performed on the ITT population. Subjects will be analyzed as randomized.
- Due to the inclusion criteria revision in May of 2021 for Schirmer's test parameters, the modified ITT (mITT) population includes all ITT except for those subjects that did not meet the revised eligibility at the baseline visit.
- Per Protocol Population – The per protocol (PP) population (subset of mITT) includes all subjects who have at least one follow-up visit and have no major protocol deviations, including specifically no use of dry-eye medications (Doxycycline, Xiidra). Subjects will be analyzed as treated. The primary and secondary efficacy analyses will be performed on the per protocol population.
- Safety Population – The safety population will include all subjects on whom the TearCare or Restasis is attempted. The safety population will be analyzed for all safety assessments. Subjects will be analyzed as treated.

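### The secondary endpoints are assigned to the ITT population, but the Month 6 models, with no visit term and no imputation, test only subjects who have Month 6 data

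*Combined protocol and SAP*

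**What the plan says.** **Population.** Sections 12.2 and 22.1 define ITT as all randomised subjects, and 22.1 states: "The primary and secondary efficacy analyses will be performed on the ITT population". Section 22.1 also lists the per protocol population for the same analyses, which does not change the ITT commitment.

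**Endpoint and model.** Section 22.5.5 (and 12.5.6) reads: "The secondary effectiveness endpoints include change from baseline at 6 Months for the following outcomes". For per-eye measures: "Endpoints assessed at the eye level will be analyzed with linear mixed effects models adjusting for baseline and site, and with a random subject effect". For SANDE and the Eye Dryness Score: "Endpoints assessed at the subject level will be analyzed using ANCOVA models adjusting for baseline and site". No visit or treatment-by-visit term is named. For the TBUT model, 22.5.4.1 explains the random subject effect as a device for the correlation between the two eyes.

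**Missing data.** Section 22.5.3: "No secondary effectiveness endpoints or safety endpoints will be imputed". Section 22.5.5 repeats it: "No imputation will be performed for secondary efficacy variables". Sections 12.5.5 and 12.5.6 say the same. For TBUT, by contrast, 22.5.4.1 states: "The primary analysis will use MCMC imputation to have a full accounting of the ITT population at the 6 Month visit", and adds a supportive multiple imputation under missing not at random.

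**Earlier visits.** Tables 3 and 4 schedule the following before Month 6 in both arms:

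| Endpoints | Post-baseline visits before Month 6 |
|---|---|
| MGSS, both gland counts, corneal and conjunctival staining, SANDE, Eye Dryness Score (seven) | Week 1, Month 1, Month 3 |
| Schirmer | Week 1, Month 1 |
| OPI (needs blink rate, Section 21.10) | Week 1 |

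Section 22.5.5 gives these visits a descriptive summary by group and visit.

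**The concern.** ANCOVA on Month 6 change has no outcome row for a subject without a Month 6 visit. A two-eye mixed model at Month 6 can borrow from the fellow eye, but it cannot recover a subject with neither eye measured. Both therefore estimate the difference among completers, under an ITT label.

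That matters if leaving the study is related to response. Section 7 says subjects cannot be masked, and the arms carry different burdens: twice-daily drops against office procedures. Dropout that depends on how subjects are doing, and differs by arm, is credible.

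The secondary endpoints are also not merely descriptive. Section 22.3 places them in the same fixed sequence at 0.05 as the primary endpoints, with MGSS first and SANDE second among the secondaries, so an error early in the order affects every later test. The plan guards against this for TBUT and provides neither imputation nor a missing-data sensitivity analysis for the secondaries.

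**Working it through.** **1. The plan's own figure.** Section 22.4.1 gives 155 per group, 10% dropout, 139 available, difference 1 s, SD 2 s, two-sided 0.05 and 98% power. Check: 155 × 0.90 = 139.5; SE = 2 × √(2/139) = 0.240; 1/0.240 − 1.96 = 2.21; power = 98.6%. The figure reproduces. It is for TBUT; no power or available N is stated for any secondary endpoint.

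**2. Subjects leaving each test.** Loss = N × d, with d = 10% (22.4.1) or about 11% (the August 2022 update in 12.7), and N = 310 (22.4.1) or 350 (12.7). These are planning rates, not observed missingness.

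| N | d = 10% | d = 11% |
|---|---|---|
| 310 | 31 | 34.1 |
| 350 | 35 | 38.5 |

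**3. Precision.** SE inflation = 1/√(1 − d) = 1.054 at 10% and 1.060 at 11%. Suppose every dropout had one earlier visit with assumed correlation ρ to Month 6. The relative variance of a group mean is then (1 − ρ²)/(1 − d) + ρ². At d = 0.11 and 175 per group:

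- ρ = 0.3: 1.1125, effective n = 157
- ρ = 0.5: 0.75/0.89 + 0.25 = 1.093, effective n = 160
- ρ = 0.7: 1.063, effective n = 165

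The complete-case n is 175 × 0.89 = 155.75. Little information is recovered, so precision is not the argument.

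**4. Bias.** The documents give no secondary-endpoint correlations and no dropout mechanism, so both are assumed. Setting: SANDE, 155 per arm, no true difference, 2,000 simulated trials per setting, baseline and post-baseline visits with equal correlation 0.5 or 0.7. Control dropout is logistic in the Month 3 score (slope 1.0-1.5 per SD); TearCare dropout is random. The SD is 31.0, taken from the SANDE change reported for the TearCare arm of the 2019 study (5.2.4). It is used as the per-visit SD, which equals the SD of change only at correlation 0.5; at 0.7 the implied SD of change is 31.0 × √(2 × 0.3) = 24.0.

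- Completer ANCOVA bias: about 0.6-1.1 points with 11% dropout in each arm, and up to about 1.4 points with 16% control and 6% TearCare.
- Analysis using earlier visits under missing at random: bias about 0.1 point or less.
- Empirical SE for both: about 2.6-3.2. This agrees with 31.0 × √(1 − ρ²) × √(2/138): 3.23 at ρ = 0.5 and 2.67 at ρ = 0.7.
- Bias relative to SE: about 0.2-0.45.

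**5. Direction.** Poor-scoring controls leave, so the remaining controls look better and the TearCare advantage shrinks. The rate of false TearCare superiority in this scenario was about 1%, below the nominal 2.5%. Selective loss of poor responders from the TearCare arm would push the other way.

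**The case against.** **The choice is disclosed and secondary.** The plan says consistently, in four places, that secondary endpoints are not imputed. It reserves full ITT accounting for TBUT, on which success depends. This stands as far as study success goes. It does not reconcile the ITT assignment with models that drop subjects.

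**Month 6-only is inferred.** The SAP does not say so outright. The reading rests on the endpoint definition, the absence of a visit term and the stated purpose of the random effect. No section describes a repeated-visit model, and the reference in 22.5.3 to what the mixed model handles by itself is tied to the primary analysis.

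**The simulation suits the remedy.** Dropout there depends only on an observed score, which is what a repeated-measures model corrects. That is fair: the small residual bias follows from the assumption, and the remedy needs a missing-not-at-random analysis beside it.

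**The Month 5 procedure.** TearCare is repeated between the Month 3 assessment and Month 6, so a model built on earlier visits credits that procedure to TearCare subjects who left before it. Assume a 10-point Month 5 gain and 11% loss before Month 5. Relative to all randomised subjects as actually treated, the earlier-visit estimate then favours TearCare by 0.11 × 10 = 1.1 points, and the completer estimate by only 0.3. But completers carry the same 1.1; it is partly cancelled by about 0.8 of opposite selection bias (1.1 − 0.8 = 0.3). With random dropout the two methods carry the same Month 5 bias. The objection calls for a sensitivity analysis; it does not favour the planned model.

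**Readings that go too far.** A reader might infer that three earlier visits are ignored for all nine endpoints; Schirmer has two and OPI one, all are summarised descriptively, and nobody who leaves before Week 1 can be recovered. A reader might infer that the bias inflates the TearCare claim; the scenario examined does the opposite. A reader might take one in nine as the loss; that is the possible 11% in 12.7, while the SAP's 10% is one in ten.

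**Conclusion.** The concern holds. The secondary tests are assigned to ITT but, as specified, are tests of Month 6 completers, with no missing-data sensitivity analysis. At planned dropout about 10-11% of randomised subjects leave each test. The illustrative bias for SANDE is modest and rests on assumed correlations, an assumed dropout mechanism and one endpoint of nine. Its direction in practice is unknown. The documents do not support a reading that the primary conclusion is at risk or that the secondary results are bound to favour TearCare. The change is worth making because the data are already collected, the plan already accepts the principle for TBUT, and the secondary endpoints share the confirmatory sequence.

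**What to change.** In 12.5.6 and 22.5.5, make the confirmatory analysis of each secondary endpoint a repeated-measures mixed model over its scheduled visits to Month 6. Include treatment-by-visit, baseline-by-visit and site, with an unstructured covariance across visits and a subject/eye effect for eye-level measures. Test the Month 6 contrast.

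Extending the MCMC imputation planned for TBUT is an acceptable equivalent. If that route is taken, amend the statements excluding imputation in 12.5.5, 12.5.6, 22.5.3 and 22.5.5.

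Keep the planned ANCOVA and mixed models on observed Month 6 data as supportive. Add the missing-not-at-random analysis already planned for TBUT, including a version that does not credit the Month 5 procedure to TearCare subjects who left before it.

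The cost is SAP wording and a little more programming, with no new data. The main secondary analysis would rely on missing at random given the earlier visits, and it can do little for OPI, which has only Week 1 to draw on.

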## **22.6 SAFETY ANALYSIS**

All adverse events will be reported by treatment group and AE category. Any serious adverse events will be completely described in the study report. The primary safety endpoint will be summarized for each treatment group.

We will compute the incidence of ocular events in two ways: first as a simple proportion, counting the number of subjects with any event (that is, counting the first event per person in either eye), then as an incidence rate, counting all events including repeated events per subject.

### **22.6.1 INTERIM ANALYSES**

No interim analyses are planned for this study.

## 23 APPENDIX D - DECLARATION OF HELSINKI

### I. PREAMBLE

1. The World Medical Association (WMA) has developed the Declaration of Helsinki as a statement of ethical principles for medical research involving human subjects, including research on identifiable human material and data.

The Declaration is intended to be read as a whole and each of its constituent paragraphs should be applied with consideration of all other relevant paragraphs.

2. Consistent with the mandate of the WMA, the Declaration is addressed primarily to physicians. The WMA encourages others who are involved in medical research involving human subjects to adopt these principles.

### II. GENERAL PRINCIPLES

1. The Declaration of Geneva of the WMA binds the physician with the words, "The health of my patient will be my first consideration," and the International Code of Medical Ethics declares that, "A physician shall act in the patient's best interest when providing medical care."
2. It is the duty of the physician to promote and safeguard the health, well-being and rights of patients, including those who are involved in medical research. The physician's knowledge and conscience are dedicated to the fulfilment of this duty.
3. Medical progress is based on research that ultimately must include studies involving human subjects.
4. The primary purpose of medical research involving human subjects is to understand the causes, development and effects of diseases and improve preventive, diagnostic and therapeutic interventions (methods, procedures and treatments). Even the best proven interventions must be evaluated continually through research for their safety, effectiveness, efficiency, accessibility and quality.
5. Medical research is subject to ethical standards that promote and ensure respect for all human subjects and protect their health and rights.

6. While the primary purpose of medical research is to generate new knowledge, this goal can never take precedence over the rights and interests of individual research subjects.
7. It is the duty of physicians who are involved in medical research to protect the life, health, dignity, integrity, right to self-determination, privacy, and confidentiality of personal information of research subjects. The responsibility for the protection of research subjects must always rest with the physician or other health care professionals and never with the research subjects, even though they have given consent.
8. Physicians must consider the ethical, legal and regulatory norms and standards for research involving human subjects in their own countries as well as applicable international norms and standards. No national or international ethical, legal or regulatory requirement should reduce or eliminate any of the protections for research subjects set forth in this Declaration.
9. Medical research should be conducted in a manner that minimizes possible harm to the environment.
10. Medical research involving human subjects must be conducted only by individuals with the appropriate ethics and scientific education, training and qualifications. Research on patients or healthy volunteers requires the supervision of a competent and appropriately qualified physician or other health care professional.
11. Groups that are underrepresented in medical research should be provided appropriate access to participation in research.
12. Physicians who combine medical research with medical care should involve their patients in research only to the extent that this is justified by its potential preventive, diagnostic or therapeutic value and if the physician has good reason to believe that participation in the research study will not adversely affect the health of the patients who serve as research subjects.
13. Appropriate compensation and treatment for subjects who are harmed as a result of participating in research must be ensured.

### III. RISKS, BURDENS AND BENEFITS

- In medical practice and in medical research, most interventions involve risks and burdens.

Medical research involving human subjects may only be conducted if the importance of the objective outweighs the risks and burdens to the research subjects.

- All medical research involving human subjects must be preceded by careful assessment of predictable risks and burdens to the individuals and groups involved in the research in comparison with foreseeable benefits to them and to other individuals or groups affected by the condition under investigation.

Measures to minimize the risks must be implemented. The risks must be continuously monitored, assessed and documented by the researcher.

- Physicians may not be involved in a research study involving human subjects unless they are confident that the risks have been adequately assessed and can be satisfactorily managed.

When the risks are found to outweigh the potential benefits or when there is conclusive proof of definitive outcomes, physicians must assess whether to continue, modify or immediately stop the study.

## IV. VULNERABLE GROUPS AND INDIVIDUALS

- Some groups and individuals are particularly vulnerable and may have an increased likelihood of being wronged or of incurring additional harm.

All vulnerable groups and individuals should receive specifically considered protection.

- Medical research with a vulnerable group is only justified if the research is responsive to the health needs or priorities of this group and the research cannot be carried out in a non-vulnerable group. In addition, this group should stand to benefit from the knowledge, practices or interventions that result from the research.

## V. SCIENTIFIC REQUIREMENTS AND RESEARCH PROTOCOLS

- Medical research involving human subjects must conform to generally accepted scientific principles, be based on a thorough knowledge of the scientific literature, other relevant sources of information, and adequate laboratory and, as appropriate, animal experimentation. The welfare of animals used for research must be respected.

- The design and performance of each research study involving human subjects must be clearly described and justified in a research protocol.

The protocol should contain a statement of the ethical considerations involved and should indicate how the principles in this Declaration have been addressed. The protocol should include information regarding funding, sponsors, institutional affiliations, potential conflicts of interest, incentives for subjects and information regarding provisions for treating and/or compensating subjects who are harmed as a consequence of participation in the research study.

In clinical trials, the protocol must also describe appropriate arrangements for post-trial provisions.

## VI. RESEARCH ETHICS COMMITTEES

- The research protocol must be submitted for consideration, comment, guidance and approval to the concerned research ethics committee before the study begins. This committee must be transparent in its functioning, must be independent of the researcher, the sponsor and any other undue influence and must be duly qualified. It must take into consideration the laws and regulations of the country or countries in which the research is to be performed as well as applicable international norms and standards but these must not be allowed to reduce or eliminate any of the protections for research subjects set forth in this Declaration.

The committee must have the right to monitor ongoing studies. The researcher must provide monitoring information to the committee, especially information about any serious adverse events. No amendment to the protocol may be made without consideration and approval by the committee. After the end of the study, the researchers must submit a final report to the committee containing a summary of the study's findings and conclusions.

